4.7 Study Monitoring

The follow-up schedule for scheduled study visits is outlined in Table 4.7a with study assessment time points described in Table 4.7b.

TABLE 4.7a. FOLLOW-UP SCHEDULE

Study Assessment Time Point	Target Day
Baseline	Up to Day -7
Pre-Transplant	Day -2 ± 1 day ¹
Day 0	Date of transplant
1 week	7 ± 2 days
2 weeks	14 ± 2 days
3 weeks	21 ± 3 days
4 weeks ²	28 ± 3 days
5 weeks ³	35 ± 3 days
6 weeks ³	42 ± 3 days
Next clinic appointment	~8 weeks (post-transplant)
14 weeks	100 ± 2 weeks

¹Assessment must occur prior to any conditioning regimen

² Research samples only can be collected ± 7 days from target day

³Assessment time points for intervention arm only

TABLE 4.7b. PATIENT CLINICAL ASSESSMENTS

Study Assessments/ Testing	Baseline	Day									
		-2	0	7	14	21	28	35	42	Next clinic appt.	100
Demographics (patient-, disease-, and treatment-related)	X										
Additional descriptive outcomes				X	X	X	X				X
Socioeconomic status	X										
Hospital Anxiety and Depression Scale (HADS)	X		X	X	X	X					
Blood draw for gene expression analysis	X	X					X				
Pregnancy test for FCBP	X										
Toxicity			X	X	X	X	X	X ¹	X ¹		
Assessment of adherence ²		X					X			X	
Heart rate and blood pressure	X		X	X	X	X	X			X	
Myeloma response assessment											X

Consent has to occur within 30 days prior to starting study drug

Numbers indicate days relative to day of transplant, with day of transplant being 0

Patients will be enrolled and randomized prior to commencement of study drug/control arm

¹ For Propranolol group only. Patients will have toxicity assessed weekly and once more 7 days \pm 3 days after discontinuing drug.

²Adherence will be assessed weekly or monthly based on number of pills prescribed.

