Eligibility: Eligible patients are between 18 and 75 years undergoing autologous HCT for treatment of multiple myeloma who are \leq 1 year since initiation of systemic anti-myeloma therapy and who have had no prior progression or relapse of myeloma prior to HCT. They must have an ECOG performance status of 0 or 1, and have a stem cell graft with $>2.0 \times 10^6$ CD34+ cells/kg available for transplant. Patients are excluded if they have had a prior autologous HCT, are on a beta-blocker at the time of study entry, have a previous intolerance to beta-blockers, have any medical contraindications to beta-blockers therapy, or have active depression.

Treatment Description: Patients enrolled in this study will be randomized to either receive propranolol or not starting 7 (\pm 2) days prior to transplant and continuing through 28 days post-transplant. Propranolol will start at 20mg

twice daily and will be titrated to 40mg twice daily as tolerated.

Accrual Objective: 40 patients will be enrolled to the clinical trial.

Accrual Period: The estimated accrual period is 9 months.

Study Duration: It is estimated that the entire duration of the study will not exceed one year as follow-up is 30-45 days.

Glossary of Study Abbreviations

AE:	adverse events
ANC:	absolute neutrophil count
CC:	Cancer Center
CR:	complete response
CRC:	clinical research coordinator
CTCAE:	Common Terminology Criteria for Adverse Events
CTRA:	conserved transcriptional response to adversity
DSM:	Data and Safety Monitoring
DSMC:	Data and Safety Monitoring Committee
ECOG:	Eastern Cooperative Oncology Group
FCBP:	Female of Child Bearing Potential
G-CSF:	granulocyte-colony stimulating factor
HADS:	Hospital Anxiety and Depression Scale
HCT:	hematopoietic stem cell transplantation
HED:	human equivalent dose
ICSR:	Individual Case Safety Reports
IMWG:	International Myeloma Working Group
IRB:	Institutional Review Board
MCW:	Medical College of Wisconsin
MM:	multiple myeloma
nCR:	near complete response
OS:	overall survival
PFS:	progression-free survival
PI:	Principal Investigator
SES:	socioeconomic status
sCR:	stringent complete response
SNS:	sympathetic nervous system
TRM:	treatment-related mortality
UCLA:	University of California Los Angeles
VGPR:	very good partial response

Table of Contents

1.0 BACKGROUND AND RATIONALE	7
1.1 Beta-adrenergic signaling in the tumor microenvironment	7
1.2 Beta-blockade and cancer	7
1.3 Propranolol dosing for cancer control	8

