2.4.3 Beta-blocker weaning

Beta-blocker will be weaned for one of three reasons: 1) completion of drug intervention (28 ± 2 days post-transplant), 2) intolerance secondary to side effects, or 3) onset of new medical symptoms rendering beta-blocker therapy as contraindicated (see section 2.3.2). For patients that are at 40 mg twice daily at the time of weaning, the dose will be reduced to 20 mg twice daily for one week before being discontinued entirely. For patients who are on 20 mg twice daily at the time of weaning, their dose will be stopped altogether.

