Drug adherence will be measured as a percentage of the prescribed number of pills that were actually taken (either 20 mg or 40 mg twice daily). This will be determined outpatient via pill count on Day -2 and Day +28 and inpatient through nursing documentation. Patients will have one additional pill count upon return of the study supply of propranolol. The return will occur at the next earliest clinic appointment following discontinuation of the propranolol. There is no consensual standard for what constitutes adequate adherence. Clinical trials report average adherence rates of 43 to 78 percent among patients taking drugs for chronic conditions; some clinical trials define rates above 80% as acceptable.⁴³ A target adherence rate of 80% will be utilized in this study to constitute having adequately retained the patient in the study. Adherence will be recorded as a continuous (0-100%) variable. Adherence will be assessed separately during two time periods – prior to transplant (between Time 1 and Time 2) and from transplant through Day +28 (Time 2 to Time 3). Patients will be included in final analyses if and only if they have been adherent (at least 80% of the prescribed dose) to the study drug during the designated time period.

As the retention rate (participants' ability or inability to be maintained on the study drug) will necessarily be affected by side effects, we will collect side effect data to better

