4.4 Specimen Collection

The Cancer Center Lab draw blood to be stored in PAXGene RNA tubes at three study time points as described in Table 4.7b. These time points include baseline (Day -7), Day -2 (immediately prior to transplant, central line placement, or administration of any conditioning regimen), and Day +28. Blood will be drawn at one of two locations: in the hospital (if participants are immediately post-transplant and/or still or re-hospitalized) or in the transplant clinic during their regular visits. The PAXGene RNA tubes do not require any additional processing of blood samples before being frozen and sent to UCLA. These PAXGene RNA tubes will be stored at -80C in the Neuroscience Research Center, which is a locked facility, until they are batched and shipped to University of California Los Angeles (UCLA) for gene expression analysis. Before being stored they will be assigned a dummy ID that will be the sole identifier of the samples. The linked identifiers will be stored on a secure computer network through the CIBMTR under the PI's name. Samples will be packaged with dry ice and shipped overnight to [name] lab at UCLA at the time of study conclusion. This will be done on a day such that the UCLA lab can receive and keep the samples frozen at -80C. Our groups have collaborated successfully on transfer of samples in the past. All samples will be sent together.

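### The Day +28 gene-expression sample may be drawn after the last propranolol dose and would still be analysed as exposed

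*Combined protocol and SAP*

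**What the plan says.** **Sampling.** Table 4.7a gives the four-week visit a window of 28 ± 3 days. Footnote 2 widens it for gene-expression blood: "Research samples only can be collected ± 7 days from target day".

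**End of drug.** Section 2.4.3 lists as the first reason for weaning "completion of drug intervention (28 ± 2 days post-transplant". What follows depends on dose. At 40 mg twice daily, "the dose will be reduced to 20 mg twice daily for one week before being discontinued entirely". At the lower dose there is no taper: "For patients who are on 20 mg twice daily at the time of weaning, their dose will be stopped altogether". The synopsis has treatment "continuing through 28 days post-transplant".

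**Order of draw and drug.** Section 4.4 places the Day -2 sample "immediately prior to transplant, central line placement, or administration of any conditioning regimen", and Table 4.7a footnote 1 repeats the requirement about conditioning. For the third sample, 4.4 names only Day +28.

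**Who counts as exposed.** Section 2.4.1 keeps patients who remain at 20 mg twice daily in the exposed group for gene expression. Section 5.3.1 admits intervention patients who are 80% adherent at either dose, so that those analysed have had enough drug. Section 3.2.2.1b defines adherence as the share of prescribed pills that were taken.

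**Role of the time point.** Section 5.1.2 names Day +28 as the primary endpoint, and 3.1 makes it one of two comparison times. Section 5.2 says the study is mainly meant to produce effect-size estimates for planning later work.

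**The concern.** The Day +28 comparison is meant to contrast patients on propranolol with controls. The draw window runs five days beyond the latest planned completion day, and no rule ties the draw to the last dose. A sample can therefore comply with the protocol, come from a patient who has stopped the drug, and enter the exposed group. If the effect on expression fades after stopping, such samples pull the estimated difference toward zero, in a pilot whose main product is that estimate. Section 5.3.1 has no step that would detect this.

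**Working it through.** The plan gives no figure of its own to reproduce, so the check is date arithmetic.

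**Inputs**
- Draw day d = 21 to 35 (28 ± 7, Table 4.7a footnote 2): 15 days.
- Completion day s = 26 to 30 (28 ± 2, section 2.4.3): 5 days.
- Time at reduced dose after completion: 0 days at 20 mg twice daily, 7 days at 40 mg twice daily (2.4.3).
- Section 2.4.3 does not say what the completion day is. Reading A takes it as the last full-dose day, L = s (compatible with the synopsis). Reading B takes it as the first day without full dose, L = s - 1.

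**Formulas.** Gap g = d - L. At 20 mg twice daily the patient is off drug for g days when g > 0. At 40 mg twice daily the patient is at the reduced dose for g = 1 to 7, and off drug for g - 7 days when g > 7.

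**Longest permitted interval off drug** (s = 26, d = 35)
- Reading A: g = 35 - 26 = 9. Off drug 9 days at 20 mg, and 9 - 7 = 2 days at 40 mg.
- Reading B: g = 35 - 25 = 10. Off drug 10 days at 20 mg, and 10 - 7 = 3 days at 40 mg.

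**Permitted day pairs** (15 × 5 = 75). These count what the rules allow; they are not frequencies.

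| | Reading A | Reading B |
|---|---|---|
| Draw after last full-dose day | 9+8+7+6+5 = 35 | 10+9+8+7+6 = 40 |
| 20 mg twice daily: off drug | 35 | 40 |
| 40 mg twice daily: off drug | 2+1 = 3 | 3+2+1 = 6 |
| 40 mg twice daily: reduced dose | 35 - 3 = 32 | 40 - 6 = 34 |

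The concern is therefore mainly about patients held at 20 mg twice daily. The ± 3 day visit window would shorten the gap but not close it: with d = 25 to 31 the longest gap is 31 - 26 = 5 days (A) or 31 - 25 = 6 days (B). Both are under 8, so no patient on 40 mg would be off drug.

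**Adherence filter.** Take a patient at 20 mg twice daily who takes every pill, completes on Day +26 and is sampled on Day +35. Pills taken divided by pills prescribed is 100%. The nine drug-free days carry no prescribed pills, so they do not lower the figure, and the sample passes.

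**Dilution, for scale only.** If k of the 15 targeted intervention samples (5.2) are off drug and have lost a fraction r of the effect, the expected difference shrinks by k × r / 15. The documents give neither k nor r. Assuming k = 0 to 3 and r = 0 to 1, the range is 0% to 3 × 1 / 15 = 20%.

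**The case against.** The intended order can be inferred. The synopsis continues treatment to Day 28, 5.1.2 describes weaning as additional follow-up after the endpoint, and Table 4.7b puts the blood draw and an adherence check in the same Day 28 column. If blood is drawn at that visit and drug ends then or later, no sample is late. Figure 1 may also state the order. Completion day and draw day are probably linked, so counting day pairs as if they were independent says nothing about how often late draws occur. An off-drug sample needs a late draw and, in most permitted combinations, a patient held below the target dose. The CTRA profile is described in 5.3.1 as a shift over extended periods of stress, which does not imply rapid reversal.

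Any dilution may also be small beside the study's imprecision. Assuming a simple two-group comparison with 15 per arm, the 95% interval half-width is 2.048 × √(2/15) = 0.75 SD. For an assumed true effect of 0.5 SD, even 20% dilution is 0.10 SD, about 13% of that. For 1.0 SD it is about 27%.

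Finally, stop dates can probably be recovered. Table 4.7b footnote 1 says "Patients will have toxicity assessed weekly and once more 7 days" (± 3) after the drug is discontinued, and 3.2.2.1b adds "Patients will have one additional pill count upon return of the study supply of propranolol".

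Most of this stands, and it limits the point to a gap in the rules. It does not close the gap. Footnote 2 separates the research sample from the visit, so the shared column does not bind it. The plan states an order for Day -2 but not for Day +28. No rule in 5.3.1 uses the stop dates.

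**Conclusion.** The point holds as a cheap improvement. Followed as written, the readable text allows a Day +28 sample up to 9 days (A) or 10 days (B) after the last dose at 20 mg twice daily, and up to 2 or 3 days at 40 mg twice daily. The adherence filter would keep such samples in the exposed group. The documents do not say how often draws are late, how many patients stay at 20 mg, or how fast any effect reverses. The size of the dilution is therefore unknown and may be zero.

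A reader might infer three stronger things that the documents do not support:
- That about half of the Day +28 samples will be off drug, from 35/75 = 47%. That share counts permitted combinations, and nothing suggests they are equally likely.
- That patients sampled during the one-week reduction from 40 mg are unexposed. They are taking 20 mg twice daily, which 2.4.1 and 5.3.1 count as exposure.
- That the primary analysis as a whole is compromised. The Day -2 comparison is unaffected, and the text suggests that weaning is meant to follow the Day +28 endpoint.

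**What to change.** Change sampling and analysis rules only. Dosing and weaning stay as they are.

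1. Reconcile 2.4.3 with Table 4.7a by stating which day 28 ± 2 denotes: the last full-dose day or the first day without full dose.
2. In footnote 2 and section 4.4, state that for patients reaching planned completion the Day +28 research sample is drawn while the patient is still taking propranolol at either dose. That means no later than the day of the last dose, and preferably before the wean begins. Samples that turn out late are still collected.
3. Record the draw date in both arms and the last-dose date in the intervention arm. Keep the range of draw days similar between arms.
4. In 5.3.1, pre-specify a sensitivity analysis of the Day +28 comparison that leaves out only intervention samples drawn after the last dose.

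**Costs**
- Scheduling is tighter, mainly at 20 mg twice daily. Permitted draw days (21 to L) fall from 15 to 6-10 (A) or 5-9 (B). At 40 mg twice daily, drawing up to L + 7 within the window leaves 13-15 (A) or 12-15 (B).
- A small between-arm difference in draw day becomes possible, where the present window is the same for both arms. Section 1.2 treats the first 30 days as a period of high stress and inflammation, so this could matter. The recorded dates allow it to be checked or adjusted for.
- The sensitivity analysis loses precision. With 15 per arm and k intervention samples left out, the standard error is multiplied by √[(1/(15-k) + 1/15) / (2/15)]: 1.018 for k = 1, 1.038 for k = 2 and 1.061 for k = 3. That is 1.8% to 6.1% wider over this assumed range.

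The exclusion should not extend to reduced-dose samples. If that removed, say, 7 of 15, the same formula gives √(0.1917/0.1333) = 1.20, a 20% wider standard error, for dropping patients whom the plan regards as exposed.

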5.0 STATISTICAL ANALYSIS

5.1 Study Design

5.1.1 Accrual

It is estimated that 9 months – 1 year will be necessary to enroll the targeted sample size.

5.1.2 Primary Endpoint

The primary endpoint is Day +28 (4 weeks) following HCT for MM, with intervention arm patients followed for an additional 1-2 weeks until they are weaned from beta-blocker therapy.

5.2 Sample Size and Power Calculation

We will enroll 40 participants undergoing autologous HCT for MM at MCW. Accounting for study attrition and beta-blocker intolerance, we aim to have 30 patients with a complete set of gene data. A sample size of 40 will inform our feasibility aim, while a targeted final sample of 15 participants in the intervention group will be sufficient for gene expression analysis. The gene expression sample size is based on previous studies with similar or smaller sample sizes that have evaluated gene expression as a function of psychosocial factors and yielded hundreds of differentially expressed genes that generate statistically significant results in higher-order bioinformatics.^{35, 45, 46} More specific sample size estimates are difficult to project with any greater accuracy, as there is not data on the effect size for gene expression differences as a function of propranolol in humans. To this end, the current proposal will inform future sample size estimations. This study is intended mainly to generate effect size estimates and 95% confidence intervals to aid with planning future research projects. We will generate both simple estimates of effect size as well as adjusted estimates, attempting to control for any accidental confounding that may occur despite randomization.

5.3 Analysis of Primary Endpoints

5.3.1 Gene Expression Profiling

The final outcome for the gene expression analysis will be expression levels of the group of genes comprising the conserved transcriptional response to adversity (CTRA) profile. The CTRA profile represents a systemic shift in basal gene expression profiles among circulating immune cells during extended periods of stress, threat, or uncertainty consistent with the physiology of stress-associated illness.³²⁻³⁶ This profile is characterized by 53-genes and includes up-regulated expression of pro-inflammatory genes (*IL1A*, *IL1B*, *IL6*, *IL8*, *TNF*, *PTGS1*, *PTGS2*, *FOS*, *FOSB*, *FOSL1*, *FOSL2*, *JUN*, *JUNB*, *JUND*, *NFKB1*, *NFKB2*, *REL*, *RELA*, and *RELB*) and down-regulated expression of genes involved in type I interferon (IFN) responses (*GBP1*, *IFI16*, *IFI27*, *IFI27L1-2*, *IFI30*, *IFI35*, *IFI44*, *IFI44L*, *IFI6*, *IFIH1*, *IFIT1-3*, *IFIT5*, *IFIT1L*, *IFITM1-3*, *IFITM4P*,

IFITM5, IFNB1, IRF2, IRF7-8, MX1-2, OAS1-3, and OASL) and antibody synthesis (*IGJ, IGLL1, and IGLL3*).^{33, 34, 47, 48} This CTRA profile is significantly regulated through beta-adrenergic mediated signaling. The CTRA profile will include a composite of standardized scores on the 53 a priori defined genes and measured levels of each transcript treated as 53 repeated measurements analyzed by a mixed effect linear model with a residual covariance structure estimated to account for potential correlation among the 53 genes.

Primary analyses will be performed at the time of all 3 blood draws (Baseline, Day -2, and Day +28) and will use general linear model analyses to quantify the association between expression of each of the 53 CTRA contrast genes and beta-blocker usage. To ensure analysis of patients with sufficient beta-blocker exposure, only gene expression data from study participants with an adherence rate of 80% (at either dose) will be used as comparators against the control group. Descriptive tables of patient-, disease-, and transplant-related factors will be prepared with separate columns by propranolol vs. no propranolol groups. Any demographic or psychosocial variables (other than those of primary interest) that are unevenly distributed between groups after randomization will be adjusted for in subsequent analyses as previously described using ANCOVA. Further, differences in gene expression will be compared between groups/variables that might not have been randomly distributed, regardless of beta-blocker treatment assignment, to ascertain whether these differences may be stronger than drug-attributed changes. The UCLA Social Genomics core will provide genetic and statistical analyses for gene expression data.

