5.4 Analysis of Secondary Endpoints

5.4.1 Gene expression based on psychosocial factors

Subgroup analyses will describe additional psychosocial factors (SES, depression, anxiety) that may result in altered gene expression or differentially affect the response to beta-blockers in our proposed cohort. As this study is not powered to formally assess this relationship, these will be exploratory analyses to determine whether there is sufficient signal of a response to merit further exploration in future studies.

SES will be assessed by household income prior to diagnosis with MM as described in section 4.6.1. This information will be collected from participants at baseline/time of study enrollment. SES will be assessed by all 7 categorical levels collected as well as by lowest quartile vs. all other quartiles. Anxiety and depression will be evaluated both continuously as well as categorically with a cutoff of 8 or above signifying an abnormal level of anxiety or depression. General linear model analyses will be used to quantify the association between the three psychosocial variables of interest – SES, depression, and anxiety – with expression of the CTRA gene profile, measured continuously. Beta-blocker usage will then be entered into this model to ascertain whether it significantly changes the association between SES, depression, and anxiety and gene expression as measured by the CTRA profile. Significance will be assessed by change in magnitude of the partial regression coefficient relating candidate psychosocial variables (e.g., SES) to

the composite CTRA gene expression z-score in presence vs. absence of control for beta-blocker exposure.

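### The primary gene-expression result is not pinned to one set of draws or one model, and baseline expression is compared as a primary result but not named as a covariate

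*Combined protocol and SAP*

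**What the plan says.** **Draws.** Section 3.1 (Primary Endpoint) compares the arms at two times, shortly before transplant and 28 days after. Section 5.3.1 says "Primary analyses will be performed at the time of all 3 blood draws (Baseline, Day -2, and Day +28"), so the baseline draw is a primary comparison there. Section 5.1.2 says "The primary endpoint is Day +28 (4 weeks) following HCT for MM" and goes on to describe how long intervention patients are followed while the drug is weaned.

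**Model.** Section 5.3.1 first names the CTRA gene group as the final outcome: "The CTRA profile will include a composite of standardized scores on the 53 a priori defined genes", with "measured levels of each transcript treated as 53 repeated measurements analyzed by a mixed effect linear model". Its next paragraph says the primary analyses use general linear models to quantify "the association between expression of each of the 53 CTRA contrast genes and beta-blocker usage". Section 5.4.1 (secondary analyses) works with "the composite CTRA gene expression z-score".

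**Covariates.** Section 5.3.1 says "Any demographic or psychosocial variables (other than those of primary interest) that are unevenly distributed between groups after randomization will be adjusted for", by ANCOVA. Section 5.2 promises simple and adjusted effect sizes but lists no covariates. Neither names baseline expression.

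**Purpose.** Section 5.2 says the study is meant mainly to give effect sizes and 95% confidence intervals for planning later work.

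**The concern.** A pilot whose main product is an effect size has to say which effect size. Here a reader can arrive at different headline results depending on the paragraph followed: a profile-level estimate at each of two draws, the same at three draws, or a set of single-gene estimates at each draw. With the choice open, it can be made after the data are seen, and the figure carried into the next trial's sample size would inherit that freedom.

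The baseline draw is also in the wrong role. As a comparison between randomized arms before any drug, it can show only chance differences. As a covariate, it could narrow the interval at the later draws and offset a chance imbalance, which matters with about 15 patients per arm.

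**Working it through.** **1. Reproduce the plan's gene count.** The genes listed in section 5.3.1 are 19 pro-inflammatory, 31 interferon-related and 3 antibody-related: 19 + 31 + 3 = 53, which agrees with the plan.

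**2. Count the candidate primary estimates.**

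| Reading | Draws | Profile-level | Per-gene |
|---|---|---|---|
| 5.1.2, if it selects a draw | 1 | 1 | 53 |
| 3.1 | 2 | 2 | 106 |
| 5.3.1 | 3 | 3 | 159 |

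Of the 159, 53 sit at baseline.

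**3. Inputs for precision.** Section 5.2 aims for 30 complete sets, 15 of them in the intervention group, which leaves 15 controls. The plan gives no SD, so results are in SD units of the later draw. The correlation r between baseline and the later draw is not in the documents; I assume 0, 0.3, 0.5 and 0.7.

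**4. Half-width of the 95% CI, 15 per arm.** SE = sqrt(2/15) = 0.365 SD.

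- Unadjusted: t(28) x 0.365 = 2.048 x 0.365 = 0.748.
- ANCOVA: t(27) x 0.365 x sqrt(1 + 1/26) x sqrt(1 - r²), where the 1/26 term is the average cost of estimating the slope. At r = 0 this is 2.052 x 0.365 x 1.019 = 0.763.

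| r | Half-width with ANCOVA (SD) | Change from 0.748 |
|---|---|---|
| 0 | 0.763 | +2.1% |
| 0.3 | 0.728 | -2.6% |
| 0.5 | 0.661 | -11.6% |
| 0.7 | 0.545 | -27.1% |

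Break-even: sqrt(1 - r²) = 0.748/0.763, so r is about 0.20.

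**5. With no attrition, 20 per arm.** Unadjusted 0.640; adjusted 0.650, 0.620, 0.563 and 0.464 at the same r; break-even about 0.17.

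**6. Chance imbalance at 15 per arm.** P(baseline gap of at least 0.5 SD, either direction) = 2 x (1 - Phi(0.5/0.365)) = 0.171. A gap d, in baseline SDs, moves the unadjusted estimate by r x d. For d = 0.5 that is 0.15, 0.25 or 0.35 SD at r = 0.3, 0.5 or 0.7.

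**7. Order of baseline draw and first dose.** Section 2.4.1 starts drug at Day -7 ± 2, so as early as Day -9. Section 4.4 puts the baseline draw at Day -7, and Table 4.7a allows it up to Day -7. No section says that the blood draw comes first. If a share f of propranolol-arm baseline samples were post-dose and carried a share k of the later effect, ANCOVA would shrink the estimate by about r x f x k. At r = 0.5 and f = 0.5 that is 2.5% for k = 0.1 and 25% for k = 1; both f and k are assumptions.

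**The case against.** **A primary model is named.** A reader might infer that the plan names none. That is not so: section 5.3.1 attaches the word primary to the per-gene general linear models. What stands is that the same section gives the profile as the final outcome with a different model, and nothing ranks or links the two.

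**Section 5.1.2 is a weak third version of the draw.** It may state only follow-up timing. Section 3.2.2.1b, which speaks of gene expression in a run-in period and then during transplant, supports the two draws of section 3.1. The firm conflict is between 3.1 and 5.3.1, over baseline.

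**This is a pilot.** One might read 159 comparisons as an inflated error rate. The documents set no significance level for gene expression, so that reading lacks a basis. The objection does not remove the problem, because the pilot's stated product is the effect size and its interval.

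**The gain from baseline adjustment is unknown.** This is correct: below r of about 0.20 there is a small loss, and r may be lower at Day +28, since section 3.2.2.1b expects more confounding during transplant. Nor does omitting the covariate bias a randomized comparison. The adjusted estimates of section 5.2 could be stretched to cover a chance baseline gap, but the plan does not say so.

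**Baseline samples are probably pre-dose.** One might infer from the day windows that baseline is contaminated by drug. Section 3.2.2.1b points the other way: it counts adherence from Time 1 and separates baseline vital signs from those taken after drug starts. The 25% case in step 7 needs half of the samples to be late and the full drug effect to be present after about two days. This remains a hypothetical gap in wording.

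**Conclusion.** The concern holds in a bounded form. Sections 3.1 and 5.3.1 disagree on whether baseline is a primary comparison, and section 5.3.1 gives a profile-level outcome and per-gene primary analyses without reconciling them. The headline could be one composite estimate per draw or up to 159 single-gene estimates. Baseline expression is already collected and not named as a covariate. Using it changes the half-width at 15 per arm from 0.75 SD to between 0.76 and 0.55 SD over assumed r of 0 to 0.7, and guards against a baseline gap of 0.5 SD or more, which has about a 17% chance of arising. These figures assume 15 controls and the stated range of r.

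The plan should be changed on draws, model and the role of baseline. The draw-order point is minor. Contamination of baseline and bias from leaving out the covariate are not supported by the documents.

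**What to change.** - **One primary contrast.** Reconcile sections 3.1, 5.1.2 and 5.3.1 so that the primary result is a single profile-level contrast: the CTRA composite signed by the directions given in 5.3.1, or the equivalent mixed-model contrast. Report it at the post-baseline draws, with the sponsor naming in advance which draw is primary. Label per-gene results descriptive or FDR-controlled.
- **Baseline as covariate.** Compare the arms by ANCOVA on arm and the patient's own baseline composite. Describe the baseline draw by arm and do not test it. Standardize all draws to one common reference, for example each gene's baseline mean and SD over both arms. Report the observed r, and keep the imbalance-adjusted estimates as supplementary.
- **Draw order (minor).** State that the baseline blood draw precedes the first dose, and record both times. If some samples prove to be post-dose, add a sensitivity analysis: unadjusted, or with those samples excluded from both the covariate and the reference. Do not rely on filling them with the overall pre-dose mean. Only propranolol-arm samples can be affected, and in a simulation (r = 0.5, 15 per arm, correlation of 0.5 assumed between lateness and baseline) mean-filling gave 0.89 and 0.94 SD for a true 0.80, with 25% and 50% of samples late.

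The cost is wording in three sections and two recorded times, with no new sample or assay. Statistically it is one degree of freedom, and an interval about 2% wider if r is near 0.

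None of this repairs the selection from the adherence filter, under which "only gene expression data from study participants with an adherence rate of 80% (at either dose) will be used as comparators" against the control group. That filter applies to the propranolol arm alone and needs its own answer.
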